**Repeat all for clinical chemistry parameters (excluding serum HCG results).**

Abbreviation: QD = once daily.  
 Note: Subjects are summarized by treatment received. Results from the thyroid panel are included. Baseline is the last non-missing measurement taken before the first application of study drug.  
 Reference Listings: 16.2.8.1.1, 16.2.8.1.4

Table 14.3.5.1.2.2  
 Cohort 2: Shift from Baseline in Clinical Chemistry Laboratory Results (Standard Units) by Study Visit  
 Safety Population

Study Visit	Post-Baseline Grade	ARQ-252 Cream 0.3% QD (N=XX)					ARQ-252 Cream 0.3% BID (N=XX)				
		Missing	Low	Normal	High	Total	Missing	Low	Normal	High	Total
Week 4	Missing	XX (XX.X%)	XX (XX.X%)	XX (XX.X%)	XX (XX.X%)	XX (XX.X%)	XX (XX.X%)	XX (XX.X%)	XX (XX.X%)	XX (XX.X%)	XX (XX.X%)
	Low	XX (XX.X%)	XX (XX.X%)	XX (XX.X%)	XX (XX.X%)	XX (XX.X%)	XX (XX.X%)	XX (XX.X%)	XX (XX.X%)	XX (XX.X%)	XX (XX.X%)
	Normal	XX (XX.X%)	XX (XX.X%)	XX (XX.X%)	XX (XX.X%)	XX (XX.X%)	XX (XX.X%)	XX (XX.X%)	XX (XX.X%)	XX (XX.X%)	XX (XX.X%)
	High	XX (XX.X%)	XX (XX.X%)	XX (XX.X%)	XX (XX.X%)	XX (XX.X%)	XX (XX.X%)	XX (XX.X%)	XX (XX.X%)	XX (XX.X%)	XX (XX.X%)
	Total	XX (XX.X%)	XX (XX.X%)	XX (XX.X%)	XX (XX.X%)	XX (XX.X%)	XX (XX.X%)	XX (XX.X%)	XX (XX.X%)	XX (XX.X%)	XX (XX.X%)
Week 8	Missing	XX (XX.X%)	XX (XX.X%)	XX (XX.X%)	XX (XX.X%)	XX (XX.X%)	XX (XX.X%)	XX (XX.X%)	XX (XX.X%)	XX (XX.X%)	
	Low	XX (XX.X%)	XX (XX.X%)	XX (XX.X%)	XX (XX.X%)	XX (XX.X%)	XX (XX.X%)	XX (XX.X%)	XX (XX.X%)	XX (XX.X%)	
	Normal	XX (XX.X%)	XX (XX.X%)	XX (XX.X%)	XX (XX.X%)	XX (XX.X%)	XX (XX.X%)	XX (XX.X%)	XX (XX.X%)	XX (XX.X%)	
	High	XX (XX.X%)	XX (XX.X%)	XX (XX.X%)	XX (XX.X%)	XX (XX.X%)	XX (XX.X%)	XX (XX.X%)	XX (XX.X%)	XX (XX.X%)	
	Total	XX (XX.X%)	XX (XX.X%)	XX (XX.X%)	XX (XX.X%)	XX (XX.X%)	XX (XX.X%)	XX (XX.X%)	XX (XX.X%)	XX (XX.X%)	
Week 12	Missing	XX (XX.X%)	XX (XX.X%)	XX (XX.X%)	XX (XX.X%)	XX (XX.X%)	XX (XX.X%)	XX (XX.X%)	XX (XX.X%)	XX (XX.X%)	
	Low	XX (XX.X%)	XX (XX.X%)	XX (XX.X%)	XX (XX.X%)	XX (XX.X%)	XX (XX.X%)	XX (XX.X%)	XX (XX.X%)	XX (XX.X%)	
	Normal	XX (XX.X%)	XX (XX.X%)	XX (XX.X%)	XX (XX.X%)	XX (XX.X%)	XX (XX.X%)	XX (XX.X%)	XX (XX.X%)	XX (XX.X%)	
	High	XX (XX.X%)	XX (XX.X%)	XX (XX.X%)	XX (XX.X%)	XX (XX.X%)	XX (XX.X%)	XX (XX.X%)	XX (XX.X%)	XX (XX.X%)	
	Total	XX (XX.X%)	XX (XX.X%)	XX (XX.X%)	XX (XX.X%)	XX (XX.X%)	XX (XX.X%)	XX (XX.X%)	XX (XX.X%)	XX (XX.X%)	

Repeat this page for the remaining study drugs (ARQ-252 Cream 0.1% QD, Vehicle Cream QD, and Vehicle Cream BID), showing the same study visits shown here. Repeat all for clinical chemistry parameters (excluding serum HCG results).

Abbreviations: BID = twice daily; QD = once daily.  
 Note: Subjects are summarized by treatment received. Results from the thyroid panel are included. Baseline is the last non-missing measurement taken before the first application of study drug.  
 Reference Listings: 16.2.8.1.1, 16.2.8.1.4

Table 14.3.5.2.1.1

Cohort 1: Summary of Hematology Laboratory Results (Standard Units) by Study Visit  
Safety Population

(Same shell as Table 14.3.5.1.1.1; Reference Listing: 16.2.8.1.2)

Table 14.3.5.2.1.2

Cohort 2: Summary of Hematology Laboratory Results (Standard Units) by Study Visit  
Safety Population

(Same shell as Table 14.3.5.1.1.2; Reference Listing: 16.2.8.1.2)

Table 14.3.5.2.2.1

Cohort 1: Shift from Baseline in Hematology Laboratory Results (Standard Units) by Study Visit  
Safety Population

(Same shell as Table 14.3.5.1.2.1; Reference Listing: 16.2.8.1.2)

Table 14.3.5.2.2.2

Cohort 2: Shift from Baseline in Hematology Laboratory Results (Standard Units) by Study Visit  
Safety Population

(Same shell as Table 14.3.5.1.2.2; Reference Listing: 16.2.8.1.2)

Table 14.3.5.3.1.1

Cohort 1: Summary of Quantitative Urinalysis Laboratory Results (Standard Units) by Study Visit  
Safety Population

(Same shell as Table 14.3.5.1.1.1; Reference Listing: 16.2.8.1.3)

Table 14.3.5.3.1.2

Cohort 2: Summary of Quantitative Urinalysis Laboratory Results (Standard Units) by Study Visit  
Safety Population

(Same shell as Table 14.3.5.1.1.2; Reference Listing: 16.2.8.1.3)

Table 14.3.5.3.2.1

Cohort 1: Shift from Baseline in Quantitative and Qualitative Urinalysis Laboratory Results (Standard Units) by Study Visit  
Safety Population

(Same shell as Table 14.3.5.1.2.1; Reference Listing: 16.2.8.1.3)

Table 14.3.5.3.2.2

Cohort 2: Shift from Baseline in Quantitative and Qualitative Urinalysis Laboratory Results (Standard Units) by Study Visit  
Safety Population

(Same shell as Table 14.3.5.1.2.2; Reference Listing: 16.2.8.1.3)

Table 14.3.5.3.3.1  
 Cohort 1: Summary of Qualitative Urinalysis Laboratory Results by Study Visit  
 Safety Population

Study Visit Category	Cohort 1 ARQ-252 Cream 0.3% QD (N=XX)
Parameter: XXXXXXXXXXXXXXXX (unit)	
Baseline	XX (XX.X%) XX (XX.X%)
Week 1	XX (XX.X%) XX (XX.X%) XX (XX.X%)
Week 2	XX (XX.X%) XX (XX.X%) XX (XX.X%)
Week 3	XX (XX.X%) XX (XX.X%) XX (XX.X%)

Abbreviation: QD = once daily; TNTC = too numerous to count.  
 Note: Percentages are n/Number of subjects in the Safety population within treatment received\*100. Baseline is the last non-missing measurement taken before the first application of study drug.  
 Reference Listing: 16.2.8.1.3

Table 14.3.5.3.3.2  
 Cohort 2: Summary of Qualitative Urinalysis Laboratory Results by Study Visit  
 Safety Population

Study Visit Category	Cohort 2				
	ARQ-252 Cream 0.3% QD (N=XX)	ARQ-252 Cream 0.3% BID (N=XX)	ARQ-252 Cream 0.1% QD (N=XX)	Vehicle Cream QD (N=XX)	Vehicle Cream BID (N=XX)
Baseline					
XXXXXXXXXXXX	XX (XX.X%)	XX (XX.X%)	XX (XX.X%)	XX (XX.X%)	XX (XX.X%)
XXXXXXXXXXXX	XX (XX.X%)	XX (XX.X%)	XX (XX.X%)	XX (XX.X%)	XX (XX.X%)
Week 4					
XXXXXXXXXXXX	XX (XX.X%)	XX (XX.X%)	XX (XX.X%)	XX (XX.X%)	XX (XX.X%)
XXXXXXXXXXXX	XX (XX.X%)	XX (XX.X%)	XX (XX.X%)	XX (XX.X%)	XX (XX.X%)
XXXXXXXXXXXX	XX (XX.X%)	XX (XX.X%)	XX (XX.X%)	XX (XX.X%)	XX (XX.X%)
Week 8					
XXXXXXXXXXXX	XX (XX.X%)	XX (XX.X%)	XX (XX.X%)	XX (XX.X%)	XX (XX.X%)
XXXXXXXXXXXX	XX (XX.X%)	XX (XX.X%)	XX (XX.X%)	XX (XX.X%)	XX (XX.X%)
XXXXXXXXXXXX	XX (XX.X%)	XX (XX.X%)	XX (XX.X%)	XX (XX.X%)	XX (XX.X%)
Week 12					
XXXXXXXXXXXX	XX (XX.X%)	XX (XX.X%)	XX (XX.X%)	XX (XX.X%)	XX (XX.X%)
XXXXXXXXXXXX	XX (XX.X%)	XX (XX.X%)	XX (XX.X%)	XX (XX.X%)	XX (XX.X%)
XXXXXXXXXXXX	XX (XX.X%)	XX (XX.X%)	XX (XX.X%)	XX (XX.X%)	XX (XX.X%)

Abbreviations: BID = twice daily; QD = once daily; TNTC = too numerous to count.  
 Note: Percentages are n/Number of subjects in the Safety population within treatment received\* 100. Baseline is the last non-missing measurement taken before the first application of study drug.  
 Reference Listing: 16.2.8.1.3

Table 14.3.6.1.1  
 Cohorts 1 and 2: Summary of Investigator Local Tolerability Assessment (Dermal Response) by Study Visit  
 Safety Population

Study Visit Statistic	Cohort 1		Cohort 2	
	ARQ-252 Cream 0.3% BID (N=XX)		ARQ-252 Cream 0.3% QD (N=XX)	
	Observed	Change	Observed	Change
Baseline				
n	XX		XX	XX
Mean (SD)	XX.X (X.XX)		XX.X (X.XX)	XX.X (X.XX)
Median	XX.X		XX.X	XX.X
Min, Max	XX, XX		XX, XX	XX, XX
Week 1				
n	XX	XX	NA	NA
Mean (SD)	XX.X (X.XX)	XX.X (X.XX)	NA	NA
Median	XX.X	XX.X		
Min, Max	XX, XX	XX, XX		
Week 2				
n	XX	XX	XX	XX
Mean (SD)	XX.X (X.XX)	XX.X (X.XX)	XX.X (X.XX)	XX.X (X.XX)
Median	XX.X	XX.X	XX.X	XX.X
Min, Max	XX, XX	XX, XX	XX, XX	XX, XX

**Repeat this page for the remaining Cohort 2 study drugs (ARQ-252 Cream 0.1% QD, Vehicle Cream QD, and Vehicle Cream BID), showing the same study visits shown here. Continue for the following study visits, applicable to Cohort 2 only: Week 4, Week 8, and Week 12; put "NA" in the "n" row for Cohort 1 for these visits.**

Abbreviations: BID = twice daily; NA = not applicable; QD = once daily; SD = standard deviation.  
 Note: Subjects are summarized by treatment received. The Week 1 study visit is only applicable to Cohort 1 subjects; the Week 4 through Week 12 study visits are only applicable to Cohort 2 subjects. Lower scores indicate no evidence of irritation while higher scores indicate worsening reaction. These assessments should be done prior to the study drug application in the study site. Subjects not meeting this condition on baseline visit are completely removed from the table summary. Baseline is the last non-missing measurement taken before the first application of study drug. Change from baseline is calculated as result – baseline result.  
 Reference Listing: 16.2.9.1

Table 14.3.6.1.2  
 Cohorts 1 and 2: Summary of Investigator Local Tolerability Assessment (Dermal Response) by Study Visit  
 Categorical Results  
 Safety Population

Study Visit Category	Cohort 1				Cohort 2			
	ARQ-252 Cream 0.3% QD (N=XX)	ARQ-252 Cream 0.3% QD (N=XX)	ARQ-252 Cream 0.3% BID (N=XX)	ARQ-252 Cream 0.1% QD (N=XX)	Vehicle Cream QD (N=XX)	Vehicle Cream BID (N=XX)		
Baseline	XX	XX	XX	XX	XX	XX		
0 = No evidence of irritation	XX (XX.X%)	XX (XX.X%)	XX (XX.X%)	XX (XX.X%)	XX (XX.X%)	XX (XX.X%)		
1 = Minimal erythema	XX (XX.X%)	XX (XX.X%)	XX (XX.X%)	XX (XX.X%)	XX (XX.X%)	XX (XX.X%)		
2 = Definite erythema	XX (XX.X%)	XX (XX.X%)	XX (XX.X%)	XX (XX.X%)	XX (XX.X%)	XX (XX.X%)		
3 = Erythema and papules	XX (XX.X%)	XX (XX.X%)	XX (XX.X%)	XX (XX.X%)	XX (XX.X%)	XX (XX.X%)		
4 = Definite edema	XX (XX.X%)	XX (XX.X%)	XX (XX.X%)	XX (XX.X%)	XX (XX.X%)	XX (XX.X%)		
5 = Erythema, edema and papules	XX (XX.X%)	XX (XX.X%)	XX (XX.X%)	XX (XX.X%)	XX (XX.X%)	XX (XX.X%)		
6 = Vesicular eruption	XX (XX.X%)	XX (XX.X%)	XX (XX.X%)	XX (XX.X%)	XX (XX.X%)	XX (XX.X%)		
7 = Strong reaction spreading beyond application site	XX (XX.X%)	XX (XX.X%)	XX (XX.X%)	XX (XX.X%)	XX (XX.X%)	XX (XX.X%)		
Week 1	XX	NA	NA	NA	NA	NA		
0 = No evidence of irritation	XX (XX.X%)							
1 = Minimal erythema	XX (XX.X%)							
2 = Definite erythema	XX (XX.X%)							
3 = Erythema and papules	XX (XX.X%)							
4 = Definite edema	XX (XX.X%)							
5 = Erythema, edema and papules	XX (XX.X%)							
6 = Vesicular eruption	XX (XX.X%)							
7 = Strong reaction spreading beyond application site	XX (XX.X%)							
Week 2	XX	XX	XX	XX	XX	XX		
0 = No evidence of irritation	XX (XX.X%)	XX (XX.X%)	XX (XX.X%)	XX (XX.X%)	XX (XX.X%)	XX (XX.X%)		
...	XX (XX.X%)	XX (XX.X%)	XX (XX.X%)	XX (XX.X%)	XX (XX.X%)	XX (XX.X%)		

**Continue for the following study visits, applicable to Cohort 2 only: Week 4, Week 8, and Week 12; put "NA" in the study visit row for Cohort 1 for these visits.**

Abbreviations: BID = twice daily; NA = not applicable; QD = once daily.  
 Note: Percentages are n/Number of subjects in the Safety Population within treatment received, study visit, and overall\*100. The Week 1 study visit is only applicable to Cohort 1 subjects; the Week 4 through Week 12 study visits are only applicable to Cohort 2 subjects. These assessments should be done prior to the study drug application in the study site. Subjects not meeting this condition on baseline visit are completely removed from the table summary. Baseline is the last non-missing measurement taken before the first application of study drug.  
 Reference Listing: 16.2.9.1

Table 14.3.6.1.3  
 Cohorts 1 and 2: Summary of Investigator Local Tolerability Assessment (Other Effects) by Study Visit  
 Categorical Results  
 Safety Population

Study Visit Category	Cohort 1			Cohort 2		
	ARQ-252 Cream 0.3% QD (N=XX)	ARQ-252 Cream 0.3% QD (N=XX)	ARQ-252 Cream 0.3% BID (N=XX)	ARQ-252 Cream 0.1% QD (N=XX)	Vehicle Cream QD (N=XX)	Vehicle Cream BID (N=XX)
Baseline	XX	XX	XX	XX	XX	XX
A = Slight glazed appearance	XX (XX.X%)	XX (XX.X%)	XX (XX.X%)	XX (XX.X%)	XX (XX.X%)	XX (XX.X%)
B = Marked glazing	XX (XX.X%)	XX (XX.X%)	XX (XX.X%)	XX (XX.X%)	XX (XX.X%)	XX (XX.X%)
C = Glazing with peeling and cracking	XX (XX.X%)	XX (XX.X%)	XX (XX.X%)	XX (XX.X%)	XX (XX.X%)	XX (XX.X%)
D = Glazing with fissures	XX (XX.X%)	XX (XX.X%)	XX (XX.X%)	XX (XX.X%)	XX (XX.X%)	XX (XX.X%)
E = Film of dried serous exudates	XX (XX.X%)	XX (XX.X%)	XX (XX.X%)	XX (XX.X%)	XX (XX.X%)	XX (XX.X%)
F = Small petechial erosions and/or scabs	XX (XX.X%)	XX (XX.X%)	XX (XX.X%)	XX (XX.X%)	XX (XX.X%)	XX (XX.X%)
G = No other effects	XX (XX.X%)	XX (XX.X%)	XX (XX.X%)	XX (XX.X%)	XX (XX.X%)	XX (XX.X%)
Week 1	XX	NA	NA	NA	NA	NA
A = Slight glazed appearance	XX (XX.X%)					
B = Marked glazing	XX (XX.X%)					
C = Glazing with peeling and cracking	XX (XX.X%)					
D = Glazing with fissures	XX (XX.X%)					
E = Film of dried serous exudates	XX (XX.X%)					
F = Small petechial erosions and/or scabs	XX (XX.X%)					
G = No other effects	XX (XX.X%)					
Week 2	XX	XX	XX	XX	XX	XX
A = Slight glazed appearance	XX (XX.X%)	XX (XX.X%)	XX (XX.X%)	XX (XX.X%)	XX (XX.X%)	XX (XX.X%)
...	XX (XX.X%)	XX (XX.X%)	XX (XX.X%)	XX (XX.X%)	XX (XX.X%)	XX (XX.X%)

*Continue for the following study visits, applicable to Cohort 2 only: Week 4, Week 8, and Week 12; put "NA" in the study visit row for Cohort 1 for these visits.*

Abbreviations: BID = twice daily; NA = not applicable; QD = once daily.  
 Note: Percentages are n/Number of subjects in the Safety Population within treatment received, study visit, and overall\* 100. The Week 1 study visit is only applicable to Cohort 1 subjects; the Week 4 through Week 12 study visits are only applicable to Cohort 2 subjects. These assessments should be done prior to the study drug application in the study site. Subjects not meeting this condition on baseline visit are completely removed from the table summary. Baseline is the last non-missing measurement taken before the first application of study drug.  
 Reference Listing: 16.2.9.1

Table 14.3.6.2.1  
Cohorts 1 and 2: Summary of Subject Local Tolerability Assessment by Study Visit  
Safety Population

(Same shell as Table 14.3.6.1.1; use the below footnotes)

Abbreviations: BID = twice daily; NA = not applicable; QD = once daily; SD = standard deviation.

Note: Subjects are summarized by treatment received. The Week 1 study visit is only applicable to Cohort 1 subjects; the Week 2 through Week 12 study visits are only applicable to Cohort 2 subjects. These assessments should be done 10 - 15 minutes after the application of study drug at the study site. Subjects not meeting this condition on baseline visit are completely removed from the table summary. Baseline is the first non-missing measurement taken after the first application of study drug. Change from baseline is calculated as result – baseline result.  
Reference Listing: 16.2.9.2

Table 14.3.6.2.2  
Cohorts 1 and 2: Summary of Subject Local Tolerability Assessment by Study Visit  
Categorical Results  
Safety Population

Study Visit Category	Cohort 1					Cohort 2		
	ARQ-252 Cream 0.3% QD (N=XX)	ARQ-252 Cream 0.3% QD (N=XX)	ARQ-252 Cream 0.3% BID (N=XX)	ARQ-252 Cream 0.1% QD (N=XX)	Vehicle Cream QD (N=XX)	Vehicle Cream BID (N=XX)		
Baseline	XX	XX	XX	XX	XX	XX		
0 = None (no sensation)	XX (XX.X%)	XX (XX.X%)	XX (XX.X%)	XX (XX.X%)	XX (XX.X%)	XX (XX.X%)		
1 = Mild (slight warm, tingling sensation)	XX (XX.X%)	XX (XX.X%)	XX (XX.X%)	XX (XX.X%)	XX (XX.X%)	XX (XX.X%)		
2 = Moderate (definite warm, tingling sensation)	XX (XX.X%)	XX (XX.X%)	XX (XX.X%)	XX (XX.X%)	XX (XX.X%)	XX (XX.X%)		
3 = Severe (hot, tingling/stinging sensation)	XX (XX.X%)	XX (XX.X%)	XX (XX.X%)	XX (XX.X%)	XX (XX.X%)	XX (XX.X%)		
Week 1	XX	NA	NA	NA	NA	NA		
0 = None (no sensation)	XX (XX.X%)							
1 = Mild (slight warm, tingling sensation)	XX (XX.X%)							
2 = Moderate (definite warm, tingling sensation)	XX (XX.X%)							
3 = Severe (hot, tingling/stinging sensation)	XX (XX.X%)							
Week 2	XX	XX	XX	XX	XX	XX		
0 = None (no sensation)	XX (XX.X%)	XX (XX.X%)	XX (XX.X%)	XX (XX.X%)	XX (XX.X%)	XX (XX.X%)		
...	XX (XX.X%)	XX (XX.X%)	XX (XX.X%)	XX (XX.X%)	XX (XX.X%)	XX (XX.X%)		

*Continue for the following study visits, applicable to Cohort 2 only: Week 4, Week 8, and Week 12; put "NA" in the study visit row for Cohort 1 for these visits.*

Abbreviations: BID = twice daily; NA = not applicable; QD = once daily.

Note: Percentages are n/Number of subjects in the Safety Population within treatment received, study visit, and overall\* 100. The Week 1 study visit is only applicable to Cohort 1 subjects; the Week 4 through Week 12 study visits are only applicable to Cohort 2 subjects. These assessments should be done 10 - 15 minutes after the application of study drug at the study site. Subjects not meeting this condition on baseline visit are completely removed from the table summary. Baseline is the first non-missing measurement taken after the first application of study drug.

Reference Listing: 16.2.9.2

Table 14.3.6.3.1  
Cohort 1: Summary of Vital Signs by Study Visit  
Safety Population

(Same shell as Table 14.3.5.1.1.1; study visits include Baseline, Week 1, Week 2, and Week 3; parameters include Temperature (°C), Heart Rate (bpm), Systolic Blood Pressure (mmHg), Diastolic Blood Pressure (mmHg), Height (cm), Weight (kg), and Body Mass Index (kg/m^2) [1]; use the below footnotes)

Abbreviation: QD = once daily; SD = standard deviation.

Note: Subjects are summarized by treatment received. Baseline is the last non-missing measurement taken on or before the day of first application of study drug. Change from baseline is calculated as result – baseline result.

[1] Body Mass Index (BMI) = weight (kg) / [height (m)].

Reference Listing: 16.2.9.3

Table 14.3.6.3.2  
Cohort 2: Summary of Vital Signs by Study Visit  
Safety Population

(Same shell as Table 14.3.5.1.1.2; study visits include Baseline, Week 2, Week 4, Week 8, Week 12, and Week 13; parameters include Temperature (°C), Heart Rate (bpm), Systolic Blood Pressure (mmHg), Diastolic Blood Pressure (mmHg), Height (cm), Weight (kg), and Body Mass Index (kg/m^2) [1]; use the below footnotes)

Abbreviations: BID = twice daily; QD = once daily; SD = standard deviation.

Note: Subjects are summarized by treatment received. Baseline is the last non-missing measurement taken on or before the day of first application of study drug. Change from baseline is calculated as result – baseline result.

[1] Body Mass Index (BMI) = weight (kg) / [height (m)].

Reference Listing: 16.2.9.3

Table 14.3.6.4.1.1  
Cohort 1: Summary of 12-Lead Electrocardiogram by Study Visit  
Safety Population

(Same shell as Table 14.3.5.1.1.1; study visits include Baseline and Week 2; parameters include PR Interval (msec), QRS Interval (msec), QT Interval (msec), QTcF Interval (msec), and Heart Rate (bpm); use the below footnotes)

Abbreviation: QD = once daily; SD = standard deviation.

Note: Subjects are summarized by treatment received. Baseline is the last non-missing measurement taken before the first application of study drug. Change from baseline is calculated as result – baseline result.

Reference Listing: 16.2.9.4

Table 14.3.6.4.1.2  
Cohort 2: Summary of 12-Lead Electrocardiogram by Study Visit  
Safety Population

(Same shell as Table 14.3.5.1.1.2; study visits include Baseline, Week 4, and Week 12; parameters include PR Interval (msec), QRS Interval (msec), QT Interval (msec), QTcF Interval (msec), and Heart Rate (bpm); use the below footnotes)

Abbreviations: BID = twice daily; QD = once daily; SD = standard deviation.

Note: Subjects are summarized by treatment received. Baseline is the last non-missing measurement taken before the first application of study drug. Change from baseline is calculated as result – baseline result.

Reference Listing: 16.2.9.4

Table 14.3.6.4.2.1  
 Cohort 1: Summary of 12-Lead Electrocardiogram Interpretation by Study Visit  
 Safety Population

Study Visit Category	Cohort 1	
	ARQ-252 Cream	QD (N=XX)
Baseline		
Normal		XX (XX.X%)
Abnormal (NCS)		XX (XX.X%)
Abnormal (CS)		XX (XX.X%)
Missing		XX (XX.X%)
Total		XX (XX.X%)
Week 2		
Normal		XX (XX.X%)
Abnormal (NCS)		XX (XX.X%)
Abnormal (CS)		XX (XX.X%)
Missing		XX (XX.X%)
Total		XX (XX.X%)

Abbreviation: CS = clinically significant; NCS = not clinically significant;  
 QD = once daily.  
 Note: Percentages are n/Number of subjects in the Safety population within treatment received\*100. Baseline is the last non-missing measurement taken before the first application of study drug.  
 Reference Listing: 16.2.9.4

Table 14.3.6.4.2.2  
 Cohort 2: Summary of 12-Lead Electrocardiogram Interpretation by Study Visit  
 Safety Population

Study Visit Category	Cohort 2			
	ARQ-252 Cream 0.3% QD (N=XX)	ARQ-252 Cream 0.3% BID (N=XX)	ARQ-252 Cream 0.1% QD (N=XX)	Vehicle Cream QD (N=XX)
Baseline				Vehicle Cream BID (N=XX)
Normal	XX (XX.X%)	XX (XX.X%)	XX (XX.X%)	XX (XX.X%)
Abnormal (NCS)	XX (XX.X%)	XX (XX.X%)	XX (XX.X%)	XX (XX.X%)
Abnormal (CS)	XX (XX.X%)	XX (XX.X%)	XX (XX.X%)	XX (XX.X%)
Missing	XX (XX.X%)	XX (XX.X%)	XX (XX.X%)	XX (XX.X%)
Total	XX (XX.X%)	XX (XX.X%)	XX (XX.X%)	XX (XX.X%)
Week 4				
Normal	XX (XX.X%)	XX (XX.X%)	XX (XX.X%)	XX (XX.X%)
Abnormal (NCS)	XX (XX.X%)	XX (XX.X%)	XX (XX.X%)	XX (XX.X%)
Abnormal (CS)	XX (XX.X%)	XX (XX.X%)	XX (XX.X%)	XX (XX.X%)
Missing	XX (XX.X%)	XX (XX.X%)	XX (XX.X%)	XX (XX.X%)
Total	XX (XX.X%)	XX (XX.X%)	XX (XX.X%)	XX (XX.X%)
Week 12				
Normal	XX (XX.X%)	XX (XX.X%)	XX (XX.X%)	XX (XX.X%)
Abnormal (NCS)	XX (XX.X%)	XX (XX.X%)	XX (XX.X%)	XX (XX.X%)
Abnormal (CS)	XX (XX.X%)	XX (XX.X%)	XX (XX.X%)	XX (XX.X%)
Missing	XX (XX.X%)	XX (XX.X%)	XX (XX.X%)	XX (XX.X%)
Total	XX (XX.X%)	XX (XX.X%)	XX (XX.X%)	XX (XX.X%)

Abbreviations: BID = twice daily; CS = clinically significant; NCS = not clinically significant; QD = once daily.  
 Note: Percentages are n/Number of subjects in the Safety population within treatment received\* 100. Baseline is the last non-missing measurement taken before the first application of study drug.  
 Reference Listing: 16.2.9.4

Table 14.3.6.5.1  
 Cohort 1: Summary of Physical Examination by Study Visit  
 Safety Population

Study Visit Body System Category	Cohort 1 ARQ-252 Cream 0.3% QD (N=XX)
Screening	
Skin	
Normal	XX (XX.X%)
Abnormal (NCS)	XX (XX.X%)
Abnormal (CS)	XX (XX.X%)
Missing	XX (XX.X%)
Total	XX (XX.X%)
Lungs	
Normal	XX (XX.X%)
Abnormal (NCS)	XX (XX.X%)
Abnormal (CS)	XX (XX.X%)
Missing	XX (XX.X%)
Total	XX (XX.X%)
Heart	
Normal	XX (XX.X%)
Abnormal (NCS)	XX (XX.X%)
Abnormal (CS)	XX (XX.X%)
Missing	XX (XX.X%)
Total	XX (XX.X%)

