4.10 Treatment Stopping Rules

If a subject has non-cutaneous adverse events of concern, clinically significant laboratory values or any condition that the Investigator determines could possibly be related to the investigational product, the Investigator should immediately contact the Medical Monitor to discuss if the subject should be discontinued from treatment with investigational product.

Treatment for any individual subject will be discontinued if the subject experiences:

- A serious adverse event (SAE) or a clinically significant non-serious AE which in the opinion of the Principal Investigator or Medical Monitor warrants discontinuation from the study for that subject's well-being.
- A treatment-emergent severe (Grade 3 or higher) laboratory abnormality (confirmed by repeat sample).
- A severe infection (Grade 3 or higher)
- An Ischemic or thromboembolic cardiovascular event (regardless of Grade)
- Any other adverse event that represents an unacceptable risk to the subject (e.g., Grade 3 or higher)

As noted above, study treatment must be discontinued immediately in the event of a female subject's pregnancy.

Treatment should be interrupted:

- If a subject develops an application site reaction with the clinical appearance of an 'irritation reaction', and with a severity of a Dermal Response Score of 5 (erythema, edema and papules) or greater on the scale of Berger and Bowman, treatment should be interrupted for up to one week and may then be resumed if the reaction has, in the opinion of the Investigator, adequately resolved.

Treatment should be discontinued:

- If the application site reaction reoccurs, treatment should be discontinued permanently, and the subject followed until the reaction resolves.

For cases of suspected allergic contact dermatitis, the Medical Monitor and Sponsor should be notified and there should be discussion about performing patch testing to further evaluate. Patch testing is encouraged in such cases.

Phase 2b (Cohort 2)

In the event of a medical emergency where unblinding is required to provide medical care to the subject, refer to the most current IRT plan and Breaking Treatment Codes ([Section 4.6.1](#)). Contact the Medical Monitor and the Sponsor promptly.

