5.1.7 Local Tolerability Assessment

The Investigator Local Tolerability Assessment will be performed according to the Schedule of Visits and Assessments ([Section 1.3](#)).

Application site reactions will be graded at the timepoints outlined in the Schedule of Visits and Assessments ([Section 1.3](#)). Irritation reactions are graded using the scale detailed in the following section ([Berger 1982](#)). **Reactions at the site of product application, which may occur post-Baseline, should be differentiated from the preexisting inflammation associated with the subject's chronic hand eczema.**

The Investigator assessments will be conducted by the Investigator prior to investigational product application in the clinic.

Dermal Response

- 0 = no evidence of irritation
- 1 = minimal erythema, barely perceptible
- 2 = definite erythema, readily visible; minimal edema or minimal papular response
- 3 = erythema and papules
- 4 = definite edema
- 5 = erythema, edema and papules
- 6 = vesicular eruption
- 7 = strong reaction spreading beyond application site

Other Effects

- A = slight glazed appearance
- B = marked glazing
- C = glazing with peeling and cracking
- D = glazing with fissures
- E = film of dried serous exudates
- F = small petechial erosions and/or scabs
- G = no other effects

The Subject Local Tolerability Assessment will be performed according to the Schedule of Visits and Assessments ([Section 1.3](#)).

This assessment will be administered by the site 10 to 15 minutes after investigational product application in the clinic.

Grade	Sensation Following Investigational Product Application
0 (none)	No sensation
1 (mild)	Slight warm, tingling sensation; not really bothersome
2 (moderate)	Definite warm, tingling sensation that is somewhat bothersome
3 (severe)	Hot, tingling/stinging sensation that has caused definite discomfort

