## **9.2. Local Tolerability Assessments**

The investigator's assessment of the application site reaction will be summarized by study visit and treatment group within cohort using both categorical methods (number and percentage of subjects with each score) as well as continuous methods (e.g., mean, median). Categorical summaries will be provided for dermal response as well as other effects. No inferential statistical tests will be performed.

The subject's assessment of the application site reaction will be summarized similarly.

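### The investigator irritation table subtracts a pre-product score whose meaning is not defined, so its Change column can show improvement despite a real product reaction

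*SAP*

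**What the plan says.** The investigator grades Dermal Response from 0 to 7. Protocol 5.1.7 fixes the timing: "The Investigator assessments will be conducted by the Investigator prior to investigational product application in the clinic". It adds that reactions at the application site, "which may occur post-Baseline, should be differentiated from the preexisting inflammation" of the eczema. Footnote d (Cohort 1) and footnote g (Cohort 2) of the schedules in protocol 1.3 repeat this. None of these places says what to record for eczema at the Baseline visit.

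The shell for SAP Table 14.3.6.1.1 has Observed and Change columns. The footnote defines both terms: "Baseline is the last non-missing measurement taken before the first application of study drug. Change from baseline is calculated as result" minus baseline result. It also gives the direction: "Lower scores indicate no evidence of irritation while higher scores indicate worsening reaction".

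The governing text does not ask for a change. Protocol 6.3.2 calls for counts, percentages and mean or median scores by visit. SAP 9.2 calls for summaries "using both categorical methods (number and percentage of subjects with each score) as well as continuous methods" such as mean and median. SAP 6.1.1 gives the subject's burning/stinging score a special post-application baseline, but has no special provision for the investigator's score.

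**The concern.** A change score is meaningful only if the same thing is measured at both times. Here the two scores may not measure the same thing. Before the first application there can be no product reaction, so a non-zero baseline score can only reflect something else, in practice the eczema. After Baseline, the investigator is asked to separate product reactions from that eczema.

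Because lower is better on this scale, a negative mean change will be read as good tolerability. Tolerability is part of the Cohort 1 primary endpoint (protocol 3.2.1, SAP 2.2.2) and is a Cohort 2 safety endpoint (SAP 2.2.2). The Cohort 1 safety and PK review precedes the start of Cohort 2 (protocol 2.4.1). Milder irritation depends on these tables, because under protocol 5.7.1 a site reaction becomes an adverse event only if it needs treatment or leads to product being paused or stopped.

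**Working it through.** The plan states no figure for this score, so there is none to reproduce. The check applies the table's own formula to the scale.

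**Inputs from the documents**
- Change = post-baseline score minus pre-product baseline score (Table 14.3.6.1.1 footnote).
- Scale 0 to 7: erythema (1-2), erythema with papules (3), edema (4), all three signs (5), vesicles (6), spread beyond the site (7) (protocol 5.1.7).
- Entry IGA of at least 2 (protocol 4.7.1). Grade 2 needs faint erythema and/or flaking, plus vesicles, swelling or cracked skin (protocol 5.2.1). Several of these signs are also Dermal Response items.
- Treatment is to be interrupted for an irritation reaction "with a severity of a Dermal Response Score of 5 (erythema, edema and papules) or greater" (protocol 4.10).

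**Three ways a site could score**
1. Eczema is scored at Baseline and excluded later. Change = irritation minus disease.
2. All inflammation is scored at every visit. Change mixes irritation with eczema clearance. An effective cream gains from this, and randomization does not remove the gain.
3. Baseline is scored 0. Change = Observed, and nothing is masked.

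**Subject level, first way**
- A real reaction means a post score of 1 to 7. With baseline 0 to 7 there are 8 x 7 = 56 pairs.
- Change is negative when baseline exceeds post: 1 + 2 + 3 + 4 + 5 + 6 = 21 of 56.
- A baseline of 7 describes spread beyond an application site and is hard to picture before any application. Without it: 21 - 6 = 15 of 56 - 7 = 49.
- Reactions of 5 or more that still give a negative change: 6 to 5 (-1), 7 to 5 (-2), 7 to 6 (-1). Those that show no change: 5 to 5, 6 to 6, 7 to 7.

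**Group level, first way**
Mean change = (fraction reacting x reaction score) - mean baseline score. Reaction rates and baseline means are assumptions, because the documents give none. The reaction score is set at 3.

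| Fraction reacting | Mean observed | Change, baseline mean 0 | 1 | 2 | 3 |
|---|---|---|---|---|---|
| 0% | 0 | 0 | -1.0 | -2.0 | -3.0 |
| 30% | 0.3 x 3 = 0.9 | +0.9 | -0.1 | -1.1 | -2.1 |
| 60% | 0.6 x 3 = 1.8 | +1.8 | +0.8 | -0.2 | -1.2 |

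The same post-baseline data can therefore give a positive or a negative mean change, depending only on how eczema was scored on Day 1.

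**The case against.** The case against rests on five arguments.

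- **The harmful convention is not written down.** Score 0 means no irritation, and before any product a site could reasonably record 0 for everyone. This stands. With an all-zero baseline the column is redundant, not wrong.
- **Raw scores remain visible.** The same table has an Observed column, Table 14.3.6.1.2 gives n (%) at each score by visit, and Listing 16.2.9.1 shows every score. This also stands and limits the harm to one column.
- **The worst cases are caught elsewhere.** If a reaction of 5 or more leads to interruption under protocol 4.10, it is an adverse event under protocol 5.7.1 whatever Change shows. This stands for those reactions, but not for milder ones.
- **No inference depends on it.** SAP 9 and 9.2 plan no tests. Under the first way of scoring, randomization, stratified by baseline IGA, makes the offset similar across Cohort 2 arms and largely protects between-arm contrasts. It does not help within-arm change, Cohort 1, or the second way of scoring.
- **Baseline scores may be low.** IGA 2 or 3 can be met by cracked skin with faint erythema or flaking, which may score only 0 or 1 on Dermal Response, and fissures belong to the separate Other Effects list. This is a fair limit on size.

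A reader might infer that the plan requires eczema to be scored at Baseline and excluded afterwards, so that an irritating cream will look like an improvement. The documents do not support that. They are silent on Baseline scoring, and the post-Baseline wording is that reactions should be differentiated, which is softer than a rule of exclusion.

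**Conclusion.** The point holds in conditional form. Depending on how sites score Day 1, Change subtracts disease from irritation, tracks eczema clearance, or repeats Observed. None of these adds information about tolerability, and the first can show improvement while real reactions occur.

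The size cannot be stated. One could assume that 20% to 60% of an arm has eczema scored 4 to 6 at Baseline and the rest 0. Mean change with no irritation would then run from -(0.2 x 4) = -0.8 to -(0.6 x 6) = -3.6. Nothing in the documents supports those fractions, so this is an illustration and not an estimate.

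Nor do the documents support a wider inference that the trial's tolerability conclusions are unsound. The defect is one descriptive column. Its clearest consequence is in Cohort 1, which has about 6 subjects and no vehicle arm to offset a baseline artefact.

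**What to change.** Delete the Change columns for the investigator Dermal Response score from Table 14.3.6.1.1. State in SAP 6.1.1 and 9.2 that no change from baseline is calculated for it. This brings the shell into line with protocol 6.3.2 and the existing text of SAP 9.2.

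Keep the Baseline row as description only, and summarise observed post-baseline scores. In Table 14.3.6.1.2, add each subject's worst post-baseline score with n (%) at 5 or above, the score protocol 4.10 already uses. The per-visit rows cannot give this, because a subject may reach 5 at more than one visit.

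The cost is a few lines of SAP and shell wording, one derived row and the loss of one column. No new data are needed. The change does not settle how sites scored eczema, so the observed scores should still be read with that uncertainty in mind.
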